5.5.7.2 Management of non-haematological toxicity

Management of new or worsening pulmonary symptoms

If new or worsening pulmonary symptoms (e.g. dyspnoea) or radiological abnormality occurs, an interruption in study treatment dosing is recommended and a diagnostic workup (including

[REDACTED]

a high resolution CT scan) should be performed, to exclude pneumonitis. Following investigation, if no evidence of abnormality is observed on CT imaging and symptoms resolve, then study treatment can be restarted, if deemed appropriate by the investigator. If significant pulmonary abnormalities are identified, these need to be discussed with the AstraZeneca Study Physician.

Management of nausea and vomiting

Events of nausea and vomiting are known to be associated with olaparib treatment. In study D0810C00019 nausea was reported in 71% of the olaparib treated patients and 36% in the placebo treated patients and vomiting was reported in 34% of the olaparib treated patients and 14% in the placebo treated patients. They are generally mild to moderate (CTCAE grade 1 or 2) severity, intermittent and manageable on continued treatment. The first onset generally occurs in the first month of treatment with the incidence of nausea and vomiting not showing an increase over the treatment cycles.

No routine prophylactic anti-emetic treatment is required at the start of study treatment, however, patients should receive appropriate anti-emetic treatment at the first onset of nausea or vomiting and as required thereafter, in accordance with local treatment practice guidelines. As per international guidance on antiemetic use in cancer patients (ESMO, NCCN), generally a single agent antiemetic should be considered eg dopamine receptor antagonist, antihistamines, dexamethasone.

Interruptions for intercurrent non-toxicity related events

Study treatment dose interruption for conditions other than toxicity resolution should be kept as short as possible. If a patient cannot restart study treatment within 4 weeks for resolution of intercurrent conditions not related to disease progression or toxicity, the case should be discussed with AZ study physician.

All dose reductions and interruptions (including any missed doses), and the reasons for the reductions/interruptions are to be recorded in the eCRF.

Study treatment should be stopped at least 3 days prior to planned surgery. After surgery study treatment can be restarted when the wound has healed. No stoppage of study treatment is required for any biopsy procedure.

Study treatment should be discontinued for a minimum of 3 days before a patient undergoes radiation treatment. Study treatment should be restarted within 4 weeks as long as any bone marrow toxicity has recovered.

5.5.8 Management of toxicity of chemotherapy

Information on dosing and management of toxicity of capecitabine, vinorelbine and eribulin can be found in the local package inserts supplied with the drug. The use of any marketed comparator should be according to the local label.

Hypokalemia or hypomagnesemia should be corrected prior to initiating eribulin and these electrolytes should be monitored periodically during therapy.

5.6 Concomitant and post-study treatment(s)

Any medications (with the detailed exceptions) which are considered necessary for the patient's welfare, and which it is believed will not interfere with the study medication, may be given at the discretion of the investigator, providing the medications, the doses, dates and reasons for administration are recorded.

In addition, any unplanned diagnostic, therapeutic or surgical procedure performed during the study period must be recorded. This includes any blood transfusions.

The reasons for the use, doses and dates of treatment should be recorded in the patient's medical records and appropriate sections of the eCRF.

All medications (prescriptions or over the counter medications) continued at the start of study or started during the study or until 30 days from the end of the last protocol treatment and different from the study medication must be documented.

5.6.1 CYP3A restrictions for olaparib arm

The use of any natural/herbal products or other "folk remedies" should be discouraged but use of these products, as well as use of all vitamins, nutritional supplements and all other concomitant medications must be recorded.

Olaparib produced little/no direct inhibition in vitro of CYPs 1A2, 2A6, 2B6, 2C8, 2C9, 2C19, 2D6 or 2E1 but inhibition of CYP3A4 was seen when olaparib was tested at high concentrations, suggesting that olaparib has the potential to cause clinically relevant interactions with other CYP3A substrates in the liver or gastrointestinal tract. Induction of CYP1A2, 2B6 and 3A4 has been shown in vitro, with CYP3A4 being most likely to be induced to a clinically relevant extent. Since olaparib may reduce exposure to substrates of CYP3A through enzyme induction, the efficacy of hormonal contraceptives may be reduced if co-administered with olaparib. In vitro data have also shown that the principal enzyme responsible for the formation of the 3 main metabolites of olaparib is CYP3A4/5 and in vivo data have shown that co-administration with itraconazole (a known CYP3A inhibitor) increases olaparib AUC by an average of 2.7-fold. Consequently, to ensure patient safety, the following potent inhibitors of CYP3A must not be used during this study for any patient receiving olaparib.

While this is not an exhaustive list, it covers the known potent inhibitors, which have most often previously been reported to be associated with clinically significant drug interactions:

- ketoconazole, itraconazole, ritonavir, indinavir, saquinavir, telithromycin, clarithromycin and nelfinavir

For patients taking any of the above, the required wash-out periods prior to starting study treatment is one week.

In addition, in vivo data have shown that co-administration with rifampicin (a known CYP inducer) reduces olaparib AUC by an average of 87%. Therefore, to avoid potential reductions in exposure due to drug interactions, the following CYP3A inducers should be avoided:

- Phenytoin, rifampicin, rifapentin, rifabutin, carbamazepine, phenobarbitone, nevirapine, modafinil and St John's Wort (*Hypericum perforatum*)

For patients taking any of the above, the required wash-out periods prior to starting study treatment are phenobarbitone 5 weeks, and for any of the others, 3 weeks.

After randomisation if the use of any potent inducers or inhibitors of CYP3A are considered necessary for the patient's safety and welfare, the investigator must contact the AstraZeneca Study Physician. A decision to allow the patient to continue in the study will be made on a case-by-case basis.

5.6.2 Effect of olaparib on other drugs

Olaparib can inhibit CYP3A4 and UGT1A1 in vitro. These findings suggest that olaparib has the potential to cause clinically significant interactions with other CYP3A4 and UGT1A1 substrates in the liver or GI tract. Therefore, caution should be exercised when substrates of CYP3A4 are combined with olaparib, in particular those with a narrow therapeutic margin (eg, simvastatin, cisapride, cyclosporine, ergot alkaloids, fentanyl, pimozide, sirolimus, tacrolimus and quetiapine). Substrates of UGT1A1 should also be given with caution in combination with olaparib (eg, irinotecan, nintedanib, ezetimibe, raltegravir or buprenorphine).

Induction of CYP1A2, 2B6 and 3A4 has been shown in vitro with CYP3A4 being most likely to be induced to a clinically relevant extent. The potential for olaparib to induce CYP2C9, CYP2C19 and Pgp is unknown. It cannot be excluded that olaparib upon co-administration may reduce the exposure to substrates of these metabolic enzymes and transport protein. The efficacy of hormonal contraceptives may be reduced if co-administered with olaparib.

In vitro, olaparib has been shown to be an inhibitor of Pgp, OATP1B1, OCT1, OCT2, OAT3, MATE1 and MATE2K and is a weak inhibitor of BRCP. It cannot be excluded that olaparib may increase the exposure to substrates of Pgp (eg, statins, digoxin, dabigatran, colchicine), OATP1B1 (eg, bosentan, glibenclamide, repaglinide, statins and valsartan), OCT1 (eg, metformin), OCT2 (eg, serum creatinine), OAT3, MATE1 and MATE2K. In particular, caution should be exercised if olaparib is administered in combination with any statin.

5.6.3 Interaction of olaparib and specific co-medications

Preliminary data suggest that there is no clinically meaningful drug-drug interaction between anti-hormonal agents, tamoxifen (20 mg), anastrozole (1 mg) or letrozole (2.5 mg) when given in combination with olaparib (300 mg tablet), at steady state.

5.6.4 Anti-emetics/ Anti-diarrhoeals

Should a patient develop nausea, vomiting and/or diarrhoea, then these symptoms should be reported as AEs (see section 6.4.3) and appropriate treatment of the event given.

5.6.5 Anticoagulant Therapy

Patients who are taking warfarin may participate in this trial; however, it is recommended that prothrombin time (INR and APTT) be monitored carefully at least once per week for the first month, then monthly if the INR is stable. Subcutaneous heparin is permitted.

5.6.6 Administration of other anti-cancer agents

Patients must not receive any other concurrent anti-cancer therapy, including investigational agents, while on study treatment.

Treatment with bisphosphonates or RANKL inhibitor for the prevention of skeletal related events in patients with bone metastasis is permitted and must be started at least 5 days prior to randomisation.

5.6.7 Subsequent therapies for cancer

Details of first and subsequent therapies for cancer after discontinuation of treatment, will be collected.

The choice of subsequent systemic anticancer treatment will be entirely at the discretion of the investigator.

5.6.8 Live virus and bacterial vaccines

Live virus and bacterial vaccines should not be administered whilst the patient is receiving study medication and during the 30-day follow up period. An increased risk of infection by the administration of live virus and bacterial vaccines has been observed with conventional chemotherapy drugs and the effects with olaparib are unknown.

5.7 Treatment compliance

The administration of all study drugs (including olaparib and chemotherapy) should be recorded in the appropriate sections of the eCRF.

Patients should be given clear instructions on how and when to take their olaparib. Patients will self-administer olaparib. Study site staff will make tablet counts at regular intervals during treatment. Compliance will be assessed by the tablet count and the information will be recorded in the appropriate section of the eCRF. After the tablet count has been performed, the remaining tablets will not be returned to the patient, but will be retained by the investigative site until reconciliation is completed by the study monitor. All patients must return their bottle(s) of olaparib at the appropriate scheduled visit, when a new bottle will be dispensed. Patients will be instructed to notify study site personnel of missed doses. Dates of missed or held doses will be recorded by the site staff on the eCRF.

Patients must return all containers and any remaining tablets at the end of the study.

Chemotherapy will be administered at the study site as per standard practise and dose delays and modifications recorded in the eCRF.

5.7.1 Accountability

The study treatment provided for this study will be used only as directed in the study protocol.

The study personnel will account for all study drugs dispensed and returned.

Study site personnel, will account for all study drugs received at the site, unused study drugs and for appropriate destruction. Certificates of delivery, destruction and return should be signed. Any discrepancies must be accounted for on the appropriate forms.

5.8 Discontinuation of study treatment

Patients may discontinue study treatment in the following situations:

- Patient decision. The patient is at any time free to discontinue treatment, without prejudice to further treatment
- Objective radiological disease progression
- Adverse Event
- Severe non-compliance to study protocol
- Death

5.8.1 Procedures for discontinuation of a patient from study treatment

A patient that decides to discontinue study treatment will always be asked about the reason(s) and the presence of any adverse events. If possible, they will be seen and assessed by an investigator(s). Adverse events will be followed up (See Sections 6.4.3 and 6.4.4); questionnaires and all study drugs should be returned by the patient.

If a patient is withdrawn from study, see Section 5.9.

Any patient discontinuing study treatment should be seen at 30 days post discontinuation for the evaluations outlined in the study schedule. The patient's tumour status should be assessed clinically and, if appropriate, disease progression should be confirmed by radiological assessment. After discontinuation of study treatment, the principal investigator/sub-investigator will perform the best possible observation(s), test(s) and evaluation(s) as well as give appropriate medication and all possible measures for the safety of the patient. In addition, they will record on the eCRF the date of discontinuation, the reasons, manifestation and treatment at the time of discontinuation. Patients will be required to attend the treatment discontinuation visit. The patient should return all study medication.

After discontinuation of the study treatment at any point in the study, all ongoing AEs or SAEs must be followed until resolution unless, in the investigator's opinion the condition is unlikely to resolve due to the patients underlying disease, or the patient is lost to follow up (see Sections 6.4.3 and 6.4.4). All new AEs and SAEs occurring during the 30 calendar days after the last dose of study medication must be reported (if SAEs, they must be reported to AstraZeneca within 24 hours as described in Section 6.4.4) and followed to resolution as above. Patients should be seen at least 30 days after discontinuing study treatment to collect and / or complete AE information. Any untoward event occurring subsequent to the 30-day follow-up AE reporting period that the investigator assesses as possibly related to the study treatment should also be reported as an AE.

All patients must be followed for survival and PFS2, up to the final analysis.

5.9 Withdrawal from study

Patients are at any time free to withdraw from study (study treatment and assessments), without prejudice to further treatment (withdrawal of consent). Such patients will always be asked about the reason(s) and the presence of any adverse events. If possible, they will be seen and assessed by an investigator. Adverse events will be followed up (See Sections 6.4.3 and 6.4.4); questionnaires and all study drugs should be returned by the patient.

Withdrawn patients will not be replaced.

Reasons for withdrawal from the study:

- Voluntary withdrawal by the patient who is at any time free to discontinue their participation in the study, without prejudice to further treatment*
- Incorrectly enrolled patients i.e., the patient does not meet the required inclusion/exclusion criteria for the study
- Sponsor decision
- Patient lost to follow-up
- Death

*If a patient decides at any point in the trial that they do not wish to continue with the full study schedule of assessments but are still willing to provide important study information (e.g. disease recurrence information and/or survival status information) then the patient should continue in the study and information should continue to be collected on the clinical database. However if a patient does not wish to have any further data collected, only then should they be considered as withdrawing consent from the study. To minimise the number of cases of early withdrawal the investigator should discuss the options with the patient in case they would still be willing to undergo reduced assessments and/or reduced data collection, in which case they would remain in the study.

If a patient withdraws consent (ie no further assessment or collection of their data) they will be specifically asked if they are also withdrawing consent to the use of any of their samples (tumour and blood) taken during the trial (see section 6.6 and 6.7).

Data obtained prior to withdrawal of consent will be maintained in the clinical database and used in the study reporting.

The status of ongoing, withdrawn (from the study) and ‘lost to follow up’ patients at the time of an overall survival analysis should be obtained by the site personnel by checking the patients notes, hospital records, contacting the patients general practitioner and checking publicly available death registries. In the event that the patient has actively withdrawn consent to collection of further data the vital status of the patient can be obtained by site personnel from publicly available resources where it is possible to do so under applicable local laws.

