- i Urinalysis should be performed at screening. After screening, urinalysis will only be required if clinically indicated
- j In the event of suspected pregnancy during the study, the test should be repeated and, if positive, the patient discontinued from study treatment immediately.
- k Any patient who consents to study related Myriad *gBRCA* status testing, must also have a blood sample taken at the same time for the purpose of developing and validating a future diagnostic test(s) for *BRCA* mutations
- l Samples to be taken on Day1 only for patients with known *BRCA* mutation who have not completed PART 1 screening
- m Adverse events must be captured from time of consent. However, in Screening PART 1 of the study only SAEs related to study procedures will be collected.
- n EORTC QLQ-C30 questionnaires to be completed every 6 weeks until disease progression.
- o Healthcare Resource Use should be collected up to disease progression or treatment discontinuation (and 30 day follow-up), whichever is the latter.
- p Optional tumour biopsies to be taken during screening and at disease progression. Sample will only be submitted to the study biobank once the patient has been randomised.
- q Mandatory blood samples to be taken prior to dosing on Day 1 and at disease progression
- r Details of all anti-cancer treatments (including, but not limited to, chemotherapy and targeted agents) post discontinuation of study treatment need to be recorded
- s In addition to their regular 8 weekly contact, patients will be contacted in the 7 days following a specified date (data cut off date) for each survival analysis. The status of ongoing, withdrawn (from the study) and “lost to follow-up” patients at the time of an overall survival analysis should be obtained by the site personnel by checking the patients notes, hospital records, contacting the patients general practitioner and checking publicly available death registries. In the event that the patient has actively withdrawn consent to the processing of their personal data the vital status of the patient can be obtained by site personnel from publicly available resources where it is possible to do so under applicable local laws (see section 5.9).

-
- ^t Sample will only be submitted to the study biobank once the patient has been randomised.

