Where patients that do not meet the selection criteria are randomised in error or incorrectly started on treatment, or where patients subsequently fail to meet the study criteria post initiation, a discussion should occur between the AstraZeneca Study Team Physician and the Investigator regarding whether to continue or discontinue the patient from treatment. Once a decision is made, Investigators need to ensure they comply with all applicable requirements for human patient protection and ethical review.

The AstraZeneca Study Team Physician is to ensure all such decisions are appropriately documented. In situations where an agreement cannot be reached, the patient should have their study therapy stopped and be withdrawn from the study.

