6.6.2 Collection of blood sample for Myriad germline *BRCA1* and *BRCA2* testing

All patients must have a known deleterious or suspected deleterious *gBRCA* mutation to be randomised; this may have been determined prior to study entry or may be assessed as part of the enrolment procedure for the study (via Myriad).

6.6.2.1 Guidance for *BRCA* testing of patients with known *BRCA* status.

For patients that can be randomised to the study on the basis of a pre-existing known *gBRCA* mutation test result, a blood sample for a confirmatory *BRCA* mutation test by Myriad must be taken once the patient has consented to the study. Should the result from the Myriad test indicate the patient does not have a deleterious or suspected deleterious *BRCA* mutation, the patient can continue in the study and can continue to receive their allocated study treatment if deemed appropriate by the investigator.

Residual blood (or its derivatives) may be used to evaluate future *BRCA* companion diagnostic tests and for additional exploratory work, to elucidate the mechanism of response, understand the mode of action of study treatment, and improve the understanding of disease recurrence (including *BRCA* mutation status and its role in response).

6.6.2.2 Guidance for *BRCA* testing of patients with unknown *BRCA* status.

Patients that do not know their *BRCA* status, but meet all other eligibility criteria must have a Myriad test prior to randomisation in to the study. A blood sample for the Myriad *BRCA* test can be taken once all local ethical procedures for such testing have been completed. If the result shows that the patient has a deleterious/suspected deleterious *gBRCA* mutation, the patient can then be randomised to the study. In order to limit the time that the patient is not receiving study treatment after their last dose of chemotherapy, it may be necessary for the patient to have a Myriad *BRCA* test whilst still on chemotherapy.

Residual blood (or its derivatives) may be used to evaluate future *BRCA* companion diagnostic tests and for additional exploratory work, to elucidate the mechanism of response,

understand the mode of action of study treatment, and improve the understanding of disease recurrence (including BRCA mutation status and its role in response).

6.6.2.3 Collection of a blood sample for assessment of current and future BRCA mutation assay(s)

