7.5 Withdrawal of informed consent for donated biological samples

If a patient withdraws consent to the use of donated biological samples, the samples will be disposed of/destroyed, and the action documented. If samples are already analysed, AstraZeneca is not obliged to destroy the results of this research.

BRCA sample: As collection of the biological samples is an integral part of the study, then the patient is withdrawn from further study participation.

Archival tumour sample: Although mandatory, the patient may continue in the study if the patient is already randomised.

Tumour biopsy samples: As collection of the biological samples is an optional part of the study, then the patient may continue in the study.

Blood samples for biomarker analysis: Although mandatory, the patient may continue in the study if the patient is already randomised.

Blood sample for pharmacogenetic analysis: As collection of the biological samples is an optional part of the study, then the patient may continue in the study.

The Principal Investigator:

- Ensures patients' withdrawal of informed consent to the use of donated samples is notified immediately to AstraZeneca
- Ensures that biological samples from that patient, if stored at the study site, are immediately identified, disposed of /destroyed, and the action documented
- Ensures the laboratory(ies) holding the samples is/are informed about the withdrawn consent immediately and that samples are disposed/destroyed, the action documented and the signed document returned to the study site
- Ensures that the patient and AstraZeneca are informed about the sample disposal.

AstraZeneca ensures the central laboratory(ies) holding the samples is/are informed about the withdrawn consent immediately and that samples are disposed of/destroyed and the action documented and returned to the study site.

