12.1.1 Full analysis set

Intention to treat (ITT): The primary statistical analysis of the efficacy of olaparib will include all randomised patients and will compare the treatment groups on the basis of randomised treatment, regardless of the treatment actually received. Patients who were randomised but did not subsequently go on to receive study treatment are included in the Full Analysis Set (FAS). Therefore, all efficacy and health-related QoL data will be summarised and analysed using the FAS on an intention-to-treat (ITT) basis.

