12.3 Determination of sample size

The sample size for this study was selected to be consistent with the research hypothesis as described in Section 1.

The primary endpoint of the study is PFS. In total 230 PFS events in the study would have 90% power to show statistically significant PFS at the one-sided 2.5% level if the assumed true treatment effect were HR 0.635; this translates to an approximate 2 month clinically relevant improvement in median PFS over an assumed 4 month median PFS on chemotherapy assuming PFS is exponentially distributed.

Approximately 310 patients will be recruited (2:1 ratio) so that data maturity for the PFS analysis is approximately 75%.

It is estimated that the study recruitment period will be approximately 22 months and that 230 progression events will have occurred approximately 27 months after the first patient is randomised in the study. This will be the primary analysis of PFS. No further analyses of PFS are planned beyond this point unless requested by Health Authorities.

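### Sections 5.3, 5.9 and 7.5 let randomised patients leave progression and PFS2 follow-up without withdrawing consent to it, against Section 6.3.1; separately, the timing of known carriers' confirmatory BRCA sample is stated two ways

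*Protocol*

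**What the plan says.** **Rules that can end follow-up**
- Section 5.9 describes withdrawal from the study as covering both treatment and assessments. Its list of reasons has voluntary withdrawal as one item and, separately, "Incorrectly enrolled patients i.e., the patient does not meet the required inclusion/exclusion criteria for the study".
- Section 5.3 asks the sponsor's physician and the investigator to discuss whether a patient randomised in error continues treatment. If they cannot agree, "the patient should have their study therapy stopped and be withdrawn from the study".
- Section 7.5, on retracted consent for the BRCA sample: "As collection of the biological samples is an integral part of the study, then the patient is withdrawn from further study participation". For the archival tumour and biomarker blood samples, also mandatory, a randomised patient who retracts may stay.

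**Rules that keep patients in follow-up**
- Section 6.3.1 evaluates patients to radiological progression and then follows them for second progression and survival, whatever happens to treatment and despite protocol violations. Withdrawal of consent is the only exception.
- Section 5.8.1 requires survival and PFS2 follow-up of all patients until the final analysis.
- Section 12.1.1 says the primary efficacy analysis "will include all randomised patients and will compare the treatment groups on the basis of randomised treatment".

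**Confirmatory BRCA sample**
- Table 1, footnote l: "Samples to be taken on Day1 only for patients with known" mutation who did not go through Part 1 screening. Table 5 also gives Day 1 for patients with a local result. Section 6.2.2 defines Day 1 as the first day of treatment.
- Section 6.6.2.1 says the same sample "must be taken once the patient has consented to the study".

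**The concern.** An intention-to-treat comparison needs outcome data on everyone randomised, not only their names in the analysis set. Section 5.2 makes the allocation known to site staff. A judgement that a patient was ineligible, or a failure to agree on one, can therefore be made with the arm in view, and under Sections 5.3 and 5.9 it may end scans and PFS2 assessments for a patient who never asked to stop them. If that happens more often in one arm, or to patients with a different prognosis, censoring becomes informative.

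The BRCA point is of the same kind but smaller. If the sample is taken on the first day of treatment, whether a known carrier has a central result can depend on whether the allocated treatment was started. The centrally confirmed population would then not be fixed at baseline.

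**Working it through.** **1. The rules side by side.** Take a randomised patient who is found ineligible and is willing to be followed. Section 6.3.1 keeps the patient under RECIST, PFS2 and survival follow-up. Section 5.9 offers the same finding as a reason to leave the study, and Section 5.3 requires leaving if the two physicians disagree. The Section 5.9 safeguard (a patient who accepts reduced assessments stays in the study) is attached to voluntary withdrawal only. For a patient who retracts only the BRCA sample, Section 5.9 treats consent to follow-up and consent to sample use as separate questions, while Section 7.5 merges them. Section 6.6.2.1, by contrast, lets a known carrier whose central test does not confirm the mutation continue.

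**2. What is lost, by endpoint**
- *Analysis set:* nothing; Section 12.1.1 keeps all randomised patients.
- *OS:* little; Section 5.9 still seeks vital status for withdrawn patients.
- *PFS by central review:* scans after withdrawal do not exist. Under Section 11.1.1 a patient with no evaluable visit is censored at day 1 unless death falls within two visits of baseline (13 weeks), and an event after two or more missed visits is censored at the last evaluable assessment. A death found later through vital status therefore usually does not count in the primary PFS analysis.
- *PFS2:* recovered deaths can count; second progressions are lost.
- *Quality of life:* lost from withdrawal onward.

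**3. The design figure.** Section 12.3 states: "In total 230 PFS events in the study would have 90% power to show statistically significant PFS at the one-sided 2.5% level". The hazard ratio behind that statement is 0.635. With 2:1 allocation (Schoenfeld):

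events = (1.960 + 1.282)² / [(2/3)(1/3)(ln 0.635)²] = 10.51 / (0.2222 × 0.2062) ≈ 229.3, rounded up to 230; power at 230 events is 90.1%.

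The figure reproduces, and the fix does not change it.

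**4. Power is not the issue.** Assumption: 1, 2, 5 or 10% of the 230 events are lost and not replaced. Power would be 89.8, 89.5, 88.6 or 86.9%. Because the analysis is triggered by the event count (Section 12.2.2), longer follow-up can replace lost events. It cannot undo selection.

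**5. The planned check is coarse.** The deviation-bias analysis in Section 12.2.2.1 runs only if more than 10% of patients lacked the intended disease or received no randomised therapy: 0.10 × 310 = 31. The control arm is 310/3 ≈ 103. In the extreme case, 31 controls (31/103 = 30% of that arm) would not trigger it. The analysis excludes patients; it cannot restore scans that were not taken.

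**6. Illustration of selective loss (all rates assumed).** True HR 1; control median 4 months; follow-up uniform over 5 to 27 months; 2% of olaparib patients missing entirely; missing patients drawn from a 30% subgroup whose hazard differs from the rest.

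| Controls missing | Subgroup hazard 1.5× | Subgroup hazard 0.67× |
|---|---|---|
| 5% | 1.008 | 0.990 |
| 10% | 1.024 | 0.977 |
| 15% | 1.039 | 0.957 |

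The full-data log-rank HR was 0.998 to 1.002. The shift is modest, and its direction depends on who is lost.

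**7. BRCA sample.** Table 1 footnote c recommends starting treatment ideally within 3 days after randomisation. On the Day 1 schedule, a known carrier who is randomised and never starts may have no sample. Section 12.2.2.1 repeats the primary analysis without anyone lacking central confirmation, so that patient drops out of it. Patients of unknown status are tested before randomisation and are not exposed.

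**The case against.** The strongest case on the other side is that the protocol already protects what matters, and much of it stands.

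- A reader might infer that every patient found ineligible is removed. The text does not say so. Section 5.3 starts with a discussion about treatment and withdraws only on disagreement; Section 5.9 lists possible reasons and orders nothing; Section 6.6.2.1 lets the most foreseeable case, a mutation not confirmed centrally, continue. The right verb is may.
- A reader might infer that the intention-to-treat analysis is broken. Membership of the full analysis set is untouched and OS is largely covered. The exposure is incomplete progression, PFS2 and quality-of-life data.
- The conflict with Section 5.8.1 is softened because that section refers withdrawn patients to Section 5.9. The conflict with Section 6.3.1 is not softened: its only exception is withdrawal of consent.
- The description of withdrawal as treatment and assessments sits in the sentence on patients' own withdrawal of consent; applying it to ineligible patients is an inference. It is the natural one, since Section 5.9 gives no other meaning and Section 5.3 separates stopping therapy from leaving the study.
- Section 7.5 is triggered by the patient, not by a physician's discretion. It still ends follow-up for someone who retracted only a sample.
- A reader might infer from footnote l that the sample can be drawn on no other day. There, the word only limits which patients are sampled, and Section 6.6.2.1 allows an earlier draw. Nothing forbids a later one, and germline status does not change. What can vary is whether a result exists.

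**Conclusion.** The point holds as an internal contradiction with a bias risk, not as a demonstrated bias. Read as written, Sections 5.3, 5.9 and 7.5 may take randomised patients out of progression and PFS2 follow-up after the arm is known and without their withdrawing consent to follow-up, which Section 6.3.1 rules out.

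The size cannot be determined. The protocol gives no rate of ineligibility, disagreement, sample retraction or non-treatment, and no share of known carriers. A reader might be tempted to convert a guessed ineligibility rate into lost events, or a guessed non-treatment rate into controls missing from the confirmed population. The documents do not support either: the first would need every ineligible patient to be withdrawn before an event, the second every control to be a known carrier. Under the assumed rates shown, selective loss moves a null HR to roughly 0.96 to 1.04 in either direction.

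The sample-timing point is real but secondary. It touches only known carriers who never start treatment, and only the centrally confirmed analyses: the PFS sensitivity analysis and the secondary PFS, PFS2 and OS variables in the synopsis, which are required only if that population differs from the intention-to-treat one. The primary analysis does not depend on it.

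**What to change.** 1. In Sections 5.3, 5.9 and 7.5, state that a randomised patient found ineligible, or retracting a sample, remains in RECIST, PFS2 and survival follow-up, with the scheduled questionnaires, unless the patient withdraws consent to follow-up. Refer to Section 6.3.1 so that one rule governs. Leave the decisions on study treatment as they are.
2. Draw known carriers' confirmatory BRCA sample after consent and before randomisation. The assay can still be run afterwards, which fits the post-randomisation test described in Section 3.1. Align Table 1 with footnote l, Table 5 and Section 6.6.2.1, and move the item now listed among the on-treatment procedures in Section 6.2.2.

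Cost: amendment wording, and the same blood draw slightly earlier with some kits used on screen failures. The 310 patients, the 230 events and the analysis methods do not change.
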